DETAILED RESEARCH PROTOCOL

February 5, 2021

A. PURPOSE: *State briefly the purpose of the study; usually this will include the hypothesis, which is to be tested.*

Many older adults experience increased difficulty moving about their communities and performing one or more of their basic activities of daily living (ADLs) after undergoing a hospitalization. The purposes of this study are (1) to test the effectiveness of a mobility intervention, compared to usual care, on change in mobility after hospitalization; (2) to determine the impact on one-year outcomes (such as nursing home placement); and (3) to identify which patients benefit the most from the intervention. Ultimately, our goal is to improve recovery after hospitalization and reduce disability in hospitalized patients.

B. BACKGROUND: *Describe past studies and, if relevant, experimental or clinical findings which led to the plan for this project. This must be succinct and comprehensible without extensive reference to other material. A few pertinent references may be cited. In some cases -- e.g., as in cases where earlier studies have produced conflicting evidence -- it will be necessary to cite these studies and explain how it was decided to rely on one side or the other. For studies designed to compare or evaluate therapies, there should be a statement of the relative advantages or disadvantages of alternative modes of therapy. This section should ordinarily be less than one page long; however, when necessary it may be longer.*

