For this high-impact study, we propose to use a stepped wedge cluster randomization design on five VA hospital wards and at UAB Hospital on four hospital wards to compare a mobility program (MP) to usual care (UC) among a cohort of veterans and other patients age ≥ 50 years. We will examine pre- to post-hospital mobility and adverse outcomes including functional decline, nursing home admission, emergency department (ED) visits, hospitalization and death in the mobility program (MP) and usual care (UC) groups in the year after hospital discharge. The primary outcome of mobility will be measured by the UAB Life-Space Assessment (LSA).¹⁰⁻¹³ Secondary measures of mobility will include self-reported ability to walk $\frac{1}{4}$ mile and drive a car, as described by Gill, et al.¹⁴ We will identify patient-specific characteristics that modify the effect of the mobility intervention on post-hospital mobility and adverse outcomes to determine which hospitalized patients are most likely to benefit from this intervention.

C. SPECIFIC LOCATION OF STUDY: Where will the research take place? (When other institutions are involved it may be necessary to secure the approval of their Institutional Review Boards.)

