Our primary aim is to evaluate the impact of the mobility program on mobility in the year after hospital discharge using the UAB Life-Space Assessment (LSA). In our previous small VA-funded study of a mobility intervention, patients in the MP group had a mean LSA score that was approximately 10 points higher than in the UC group at four weeks' post-discharge. It is our expectation that the current study will replicate these results; specifically, that the 10-point difference will be apparent at 1-month post-discharge and persist thereafter. As described below, the primary statistical technique to address the primary aim will be mixed effects models. Assuming an exchangeable covariance structure across the repeated observations, a sample size of 190 participants provides greater than 90% power to detect a persistent 10-point difference in LSA scores at the $\alpha = .05$ level. We must also consider the reduced effective sample size due to clustering. It is a common practice to calculate the intraclass correlation (ICC) among clusters as a measure of how much more similar members of the same cluster are to each other than to the overall population. In this setting, we recognize that subjects at UAB may differ from subjects at the VA, leading to differences in the ICC. However, we still expect much more variability to come from individual patient factors than from the units. Using the data from our recently completed VA longitudinal study, we calculated an ICC for the LSA that rounded to 0; including data from UAB resulted in an ICC approximately 4 times larger. Assuming an ICC of 0.004 and subjects spread across 9 units, a sample size of 206 yields an effective sample size of 190 observations. In our recently completed VA longitudinal study during which patients were followed for 6 months after hospital discharge, 80% of the veterans completed at least 5 of the 6 monthly post-hospital assessments. We had 23 deaths and 3 withdrawals over the 6 months of follow-up among the 200 veterans in the study. Thus, in order to have an adequate (i.e. 206) sample size at 12-months, 258 patients will be enrolled allowing for patient losses due to

death or drop outs. Thus, while adding units from UAB to the study does increase the required sample size slightly due to the larger ICC, this is offset by the larger number of potential subjects that can be recruited.

Analytic Approach (for each specific aim)

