Informed by the modeling of secular trends, the final models will add in indicator terms for whether the observation occurred before or after the intervention, in addition to the appropriate modeling of secular trends. Additional more sophisticated modeling will evaluate the trends in the outcomes over time in the post-intervention periods to see whether temporal trends differ pre-and post- intervention. All statistical tests will be two-sided and will be considered to be significant if the associated p-value is <0.05. All analyses will be intention-to-treat based on the unit’s assignment at the time of a patient’s admission, and missing data will be imputed using a multiple imputation strategy, based on the characteristics of the data.

AIM 1: To test the effectiveness of a mobility program on recovery to pre-hospital mobility status or better and reduction of adverse outcomes in the year after hospitalization.

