To test the effectiveness of the intervention on mobility, LSA scores and changes in LSA scores for patients in the control condition will be compared to LSA scores from patients in the intervention condition. Mixed models will be used to examine and compare mean LSA over time with time considered a random effect. An indicator term will be included to denote whether the observation was from the period prior to or after implementation of the intervention. The indicator term will represent whether there was an overall difference in the LSA during the intervention period versus the pre-intervention period, and its statistical significance in the model for each outcome will be the primary test of whether the intervention had a significant effect on LSA. A priori we believe that an exchangeable covariance structure will be most suitable for the data. For the secondary hypotheses, i.e., self-reported outcomes for driving (yes/no) and ability to walk $\frac{1}{4}$ of a mile (yes/no), generalized linear mixed models (GLMMs) that account for repeated measures will be used to compare pre- and post-intervention periods. Given the randomized nature of the study design, adjustment for potential confounders will likely be unnecessary as they are expected to be equally distributed between the groups. However, as noted above, we will confirm that any potential confounders, e.g., age, length of hospitalization, and disease burden score (Cumulative Illness Rating Scale-Geriatrics, or CIRS-G²³) are indeed similar between the pre- and post-intervention periods and, should any not be, we will adjust for them in the statistical models provided they are not deemed to be consequences of the intervention.

To test the effectiveness of the intervention on adverse outcomes, we will use mixed models and GLMMs to model changes in functional decline (ADLs and IADLs), number of ED visits, and number of hospitalizations with an approach similar to the above. To test the effectiveness of the intervention on nursing home admission

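### Aim 1 names both LSA score and change in LSA, and calls the test in each model primary without saying which decides, so the 5% level for the primary question is not guaranteed

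*Protocol*

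**What the plan says.** The AIM 1 text under Analytic Approach is the same in the Protocol (section E) and the SAP on this point. It opens with two LSA quantities: "LSA scores and changes in LSA scores for patients in the control condition will be compared to LSA scores from patients" in the intervention condition. It then describes mixed models for average LSA across follow-up with a pre/post-intervention indicator, and says of that indicator that "its statistical significance in the model for each outcome will be the primary test of whether the intervention had a significant effect on LSA". The general part of the same section adds: "All statistical tests will be two-sided and will be considered to be significant if the associated p-value is <0.05".

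Other places point in different directions:

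- Protocol section A gives the purpose as testing the program "compared to usual care, on change in mobility after hospitalization". The Aim 1 title speaks of regaining the pre-hospital level. Both are relative to baseline.
- Protocol section B says "The primary outcome of mobility will be measured by the UAB Life-Space Assessment (LSA"), without saying level or change.
- Sample Size Calculations uses the level: "a sample size of 190 participants provides greater than 90% power to detect a persistent 10-point difference in LSA scores".
- Baseline LSA is listed only as a possible effect modifier in Aim 2. The covariates named for possible adjustment in Aim 1 are age, length of stay and CIRS-G, given as examples.

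**The concern.** The primary test is described as a test of an effect on LSA, and driving and walking a quarter mile are labelled secondary. So the phrase about each outcome most naturally refers to the two LSA quantities just named. On that reading there are two primary tests, each at 5%, with nothing to say which decides or what follows if they disagree. The choice could be made after both results are known, on the trial's one confirmatory question.

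The opening sentence is also faulty as a comparison. It sets scores and changes in control patients against scores alone in intervention patients.

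**Working it through.** **1. The plan's own figures.** Inputs from the Protocol's Sample Size Calculations: ICC 0.004, 9 units, 206 patients, 80% completing at least 5 of 6 visits (read as 20% loss).

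- Design effect = 1 + (206/9 − 1) × 0.004 = 1.0876. Effective N = 206/1.0876 = 189.4 (stated: 190).
- Enrolment = 206/0.80 = 257.5, so 258 (stated: 258).

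Both reproduce. The power statement cannot be checked directly, because neither the SD nor the within-person correlation is given. Working backwards, 90% power for 10 points with 95 per group needs the SD of a participant's mean LSA to be at most 21.3.

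**2. Error rate of the pair.** Take the plan's exchangeable structure with single-visit variance 1, correlation r (not stated; assumed 0.3 to 0.8), one baseline and eight follow-ups (months 1-6, 9 and 12).

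- Variance of the follow-up mean: (1 + 7r)/8.
- Variance of the mean change: (1 + 7r)/8 + 1 − 2r.
- Covariance of the two: (1 + 7r)/8 − r.

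At r = 0.5 these are 0.5625, 0.5625 and 0.0625, so the two tests correlate at 0.0625/0.5625 = 0.11. Over r = 0.3 to 0.8 the correlation runs from 0.16 to 0.06. From the bivariate normal with both tests at two-sided 0.05:

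| Rule | Chance of a false claim |
|---|---|
| Either counts, mean of eight visits | 9.7% |
| Either counts, one visit (correlation √((1−r)/2)) | 8.8% to 9.5% |
| Either counts, independent tests: 1 − 0.95² | 9.75% |
| Both required, mean of eight visits: 5% + 5% − 9.7% | 0.3% |

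A simulation of 4,000 trials per setting on the Figure 4 and 4A calendar (ward effects, linear trend, 206 patients, SD 25, assumed 60:40 VA:UAB split, r = 0.5 and 0.7) gave 9.8% to 10.1% for either and 0.2% to 0.3% for both. Each test alone held about 5%.

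If both were required, power could not exceed that of the weaker test. In a simple two-group approximation with the score test at exactly 90%, the change test has 62% power at r = 0.3 and 90% at r = 0.5.

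**3. Gap between the two estimates.** With the same patients, visits and model terms, the score estimate minus the change estimate is the estimated MP/usual-care difference in baseline LSA. Its standard error is SD × √(V/206). V is the variance factor for the MP indicator with uniform enrolment over the two calendars and ward effects in the model. VA shares from 56% to 78% were tried.

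| Time terms | V | SE, SD 20 | SE, SD 25 |
|---|---|---|---|
| Common linear trend | 11.4-11.9 | 4.7-4.8 | 5.9-6.0 |
| Linear trend by hospital | 12.7 | 5.0 | 6.2 |
| Step effects by hospital | 14.0-14.3 | 5.2-5.3 | 6.5-6.6 |

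The SE is therefore roughly half of the 10-point target. In the simulation at SD 25, the gap exceeded 5 points in about 41% of trials.

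**4. Effect of adjusting for baseline.** Subtracting baseline from the outcome when baseline is already a covariate only shifts the baseline coefficient by 1. The MP estimate is identical for score and change. Relative variances of the participant-level outcome, with the adjusted one equal to (1 + 7r)/8 − r²:

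| r | Score | Change | Baseline-adjusted |
|---|---|---|---|
| 0.5 | 0.56 | 0.56 | 0.31 |
| 0.7 | 0.74 | 0.34 | 0.25 |

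**5. Cost of keeping two primary tests.** Bonferroni at 0.025 each raises the effective N by a factor of 1.18, from 190 to 225. Clustering takes this to 225 × 0.996/(1 − 225 × 0.004/9) = 249, and 20% loss to 249/0.80, so 312 enrolled. At an effective 190, power falls from 90% to about 84%.

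**The case against.** The strongest reply is that the plan already has a single primary quantity in substance. The measure is the LSA, the technique is a mixed model, the sizing uses a difference in scores, and the indicator is described as an overall difference in LSA. No separate model for change is written out, and only the words about each outcome imply more than one model. This stands in part: the text leans towards the score, which makes the repair easy. It does not settle the matter, because the purpose and the Aim 1 title are relative to baseline and the primary-test sentence still covers more than one outcome.

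A reader might infer that the plan commits to claiming success on either result, so that the 5% level is definitely broken. The documents do not support this. No such rule is stated, and requiring both would give an error far below 5%.

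A reader might also take a gap of several points as a property of the trial. It is not a document figure. It depends on an assumed SD, uniform enrolment and complete data. Multiple imputation or adjustment for dissimilar confounders would alter it, and baseline LSA is not named for adjustment but is not excluded either.

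**Conclusion.** The point holds as a gap in specification. The plan names two LSA quantities and attaches the primary test to each, with no ranking, success rule or alpha adjustment, so the 5% level is not guaranteed. The 9-10% figure is conditional on either result counting; it changes little over the assumed correlations. The gap figure assumes an SD of 20-25 and no baseline adjustment. That range is compatible with the power statement, which at r = 0.3 to 0.8 implies a single-visit SD of at most about 34 to 23. Because this is the primary question and the remedy is wording only, it should be settled before outcome data are analysed.

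**What to change.** In the AIM 1 text of both documents:

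1. Name one primary analysis: the MP indicator in the mixed model for follow-up LSA scores (months 1-12), with unit and secular-trend terms and baseline (pre-admission) LSA as a covariate, tested two-sided at 0.05.
2. Replace the wording about the model for each outcome with a reference to this single model.
3. Label change in LSA as supportive only. With baseline in the model it gives the same MP estimate, so it still speaks to the stated purpose.
4. Rewrite the opening sentence so that the same quantity is compared in both conditions.

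Baseline adjustment is preferable to naming the unadjusted score. The unadjusted score would leave the baseline imbalance in the primary estimate and move away from the purpose and the Aim 1 title.

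The cost is a few sentences in each document. Baseline LSA is already collected on the first study day, so no new data or patients are needed and the Protocol's 190/206/258 can stand. The SAP still carries 198 and 226 for five units; that is a separate mismatch to reconcile.

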Condensed Memorial Symptom Assessment Scale (CMSAS)	5 minutes	Once
Katz ADL	3 minutes	Once
Lawton IADL	3 minutes	Once
UAB Life-Space Assessment	5 minutes	Once
Gait speed	5 minutes	Once
Step count monitoring (via StepWatch)	0 minutes (worn while in hospital)	Continuous during hospitalization
Total	21 minutes	

TABLE 3**Baseline Assessments, Part 2: to complete prior to hospital discharge**

Procedure	Length of Time Required of Participants	Frequency of Repetition
Ability to walk/drive	1 minute	Once
Fall history (previous 4 weeks)	1 minute	Once
ED visit & hospitalization history (previous 6 months)	1-6 minutes	Once
PHQ-2 (& PHQ-9, as appropriate) (depression screening tool)	2 – 6 minutes	Once
Lubben Social Network Scale	7 minutes	Once
EQ-5D-3L (quality of life index)	5 minutes	Once
Total	17-26 minutes	

Mobility Monitoring: The StepWatch® mobility monitor by Modus Health is a small (70 x 50 x 20 mm) waterproof, self-contained accelerometer pedometer that is attached loosely to the ankle via a Velcro strap and captures number of steps taken and when the steps were taken.²⁰ A StepWatch® pedometer will be applied to the ankle and will be worn for the duration of the in-hospital portion of the study by all participants. All patients in the study will wear a StepWatch to allow comparisons of mobility achieved by both the Mobility Program (MP) and Usual Care (UC) groups. Our team has extensive experience with the StepWatches, having used the device in our previous VA Merit study at the BVAMC. Flyers with the study's pager number will be placed on or near the whiteboard located in all patient rooms, and nursing will be informed of the patient's participation in the study and asked to call study staff if there are any questions about the pedometers. The pedometers will be removed as needed if they interfere with routine care, such as MRIs or other procedures.

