- Direct admission to BVAMC or UAB Hospital, or from ED (not from ICU)
- \leq 48 hours since hospital admission
- Access to a telephone after discharge

Exclusion criteria include:

- Inability to walk across a small room 2 weeks prior to admission
- Inability to stand safely with assistance
- Having a diagnosis deemed by the primary physician to be a contraindication to walking (pulmonary embolus, unstable angina, etc.)
- Being on hospice or comfort care
- Non-English speaking, blind, or deaf
- Being enrolled in other VA or UAB mobility research studies
- Isolation precautions for c. difficile, tuberculosis, radioactive treatment, or similar
- Suicidal ideation

Older adults who are either demented or delirious will have the opportunity to participate in this study. Among older adults hospitalized with acute illness, delirium and dementia are common, affecting up to 25% of the population. Exclusion of this group, who may have very different trajectories of recovery after hospitalization, would have a significant impact upon the generalizability of the research results. More importantly, this research may uncover methods by which we can improve hospital care for this vulnerable group who often do poorly when hospitalized.

Screening to determine if a participant has dementia or delirium will occur prior to signed informed consent through use of two standard assessment tools, the Mini Cognitive Assessment (Mini-Cog) and the Confusion Assessment Method (CAM). If a patient scores positively for dementia or delirium based on these tools, the patient's physician will be consulted to determine whether the patient has decision-making capacity. If there is documentation in the EMR or VISTA that the patient does not have decision-making capacity, informed consent will be sought from the appropriate legally authorized representative. Patients with dementia or delirium will be included only if they assent to the study themselves.

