To test the effectiveness of the intervention on mobility, LSA scores and changes in LSA scores for patients in the control condition will be compared to LSA scores from patients in the intervention condition. Mixed models will be used to examine and compare mean LSA over time with time considered a random effect. An indicator term will be included to denote whether the observation was from the period prior to or after implementation of the intervention. The indicator term will represent whether there was an overall difference in the LSA during the intervention period versus the pre-intervention period, and its statistical significance in the model for each outcome will be the primary test of whether the intervention had a significant effect on LSA. *A priori* we believe that an exchangeable covariance structure will be most suitable for the data. For the secondary hypotheses, i.e., self-reported outcomes for driving (yes/no) and ability to walk ¼ of a mile (yes/no), generalized linear mixed models (GLMMs) that account for repeated measures will be used to compare pre- and post-intervention periods. Given the randomized nature of the study design, adjustment for potential confounders will likely be unnecessary as they are expected to be equally distributed between the groups. However, as noted above, we will confirm that any potential confounders, e.g., age, length of hospitalization, and disease burden score (Cumulative Illness Rating Scale-Geriatrics⁵⁷) are indeed similar between the pre- and post-intervention periods and, should any not be, we will adjust for them in the statistical models provided they are not deemed to be consequences of the intervention.

To test the effectiveness of the intervention on adverse outcomes, we will use mixed models and GLMMs to model changes in functional decline (ADLs and IADLs), number of ED visits, and number of hospitalizations with an approach similar to the above. To test the effectiveness of the intervention on nursing home admission and death, we will use Cox proportional hazards models

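### The driving and quarter-mile-walk models leave out each patient's recorded pre-admission ability, which costs precision that a pre-specified baseline covariate would recover

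*Protocol*

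**What the plan says.** Under Aim 1 of the Analytic Approach (section E), the Protocol names as secondary hypotheses "self-reported outcomes for driving (yes/no) and ability to walk" a quarter mile. The method is generalized linear mixed models "that account for repeated measures will be used to compare pre- and post-intervention periods". SAP Aim 1 has the same plan ("self-reported outcomes for driving (yes/no"). Neither text restricts the denominator or includes the patient's own earlier answer.

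Other places bear on this:

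- The only mobility history that excludes a patient (section G) is "Inability to walk across a small room 2 weeks prior to admission". Nothing requires having driven or walked a quarter mile.
- Table 3 of the Protocol collects "Ability to walk/drive" at baseline. It belongs to the second part of the baseline battery, which may be completed at any time up to discharge. No analysis mentions it.
- On covariates, the default is that "adjustment for potential confounders will likely be unnecessary as they are expected to be equally distributed between the groups". Variables found dissimilar between periods are handled by the clause "should any not be, we will adjust for them in the statistical models". The examples given are "e.g., age, length of hospitalization, and disease burden score".
- Aim 1 concerns return to the patient's pre-hospital level, or beyond it. For the Life-Space Assessment (LSA), the plan looks at changes as well as scores.

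**The concern.** Raw status after discharge cannot separate a long-term non-driver from a driver who lost the ability during the illness. Both are scored no. Prior ability is probably the strongest single predictor of later ability, so leaving it out has two consequences:

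- Differences between patients that were fixed before admission stay in the residual variation and widen the confidence interval.
- If one condition happens to enrol more prior drivers, that difference stays in the estimate.

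Repeated calls do not cure this. The treatment contrast is between patients, and someone who answers the same way at every call adds between-patient variance that further calls cannot average out. At stake is the ability of two named secondary hypotheses to show anything, when the information needed is already on the case report form.

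**Working it through.** **The plan's own figures.** No rate, effect or power is stated for driving or walking. The Protocol's sample size concerns LSA and reproduces:

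- Design effect = 1 + (206/9 − 1) × 0.004 = 1.088, and 206/1.088 = 189.4 (stated as 190).
- With 20% loss, 206/0.80 = 257.5, or 258 enrolled.

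I take 206 as the number analysed.

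**Split between conditions.** From Figures 4 and 4A, assuming equal accrual per ward-month:

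- Control ward-months: VA 5+10+15+20+25 = 75; UAB 3+6+9+12 = 30; together 105.
- All ward-months: about 5 × 35.4 = 177 at the VA and 4 × 20 = 80 at UAB; together 257.
- Control share 105/257 = 41%, so about 84 usual-care (UC) and 122 mobility-program (MP) patients.

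**Assumed rates (not in the documents).** 60% previously able; 80% (UC) versus 90% (MP) of these able afterwards. The calculation is for one visit, with no clustering or calendar-time terms.

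**Formulas.** Let p be the overall proportion answering yes in a condition.

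- Unadjusted variance = Σ p(1 − p)/n over the two conditions.
- Adjusted variance ≈ Σ (within-stratum variance, averaged over prior ability)/n.

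**Case A: the previously unable never gain the ability.**

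- Proportions 0.6 × 0.80 = 48% and 0.6 × 0.90 = 54%; difference 6 points.
- Unadjusted: 0.48 × 0.52/84 + 0.54 × 0.46/122 = 0.00501; z = 0.06/0.0708 = 0.85.
- Adjusted: 0.6 × 0.16/84 + 0.6 × 0.09/122 = 0.00159; z = 0.06/0.0398 = 1.51.
- Variance ratio 0.00501/0.00159 = 3.2.

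**Case B: 15% (UC) versus 30% (MP) of the previously unable gain it.**

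- Proportions 0.48 + 0.4 × 0.15 = 54% and 0.54 + 0.4 × 0.30 = 66%; difference 12 points.
- Unadjusted: 0.54 × 0.46/84 + 0.66 × 0.34/122 = 0.00480; z = 1.73.
- Adjusted: (0.096 + 0.4 × 0.1275)/84 + (0.054 + 0.4 × 0.21)/122 = 0.00288; z = 2.24.
- Variance ratio 0.00480/0.00288 = 1.66.
- Restricting to the previously able gives z = 1.51, below the unadjusted 1.73.

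A simulation with a linear model in all patients gave variance ratios of 3.2 (A) and 1.65 (B).

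**Range.** I varied the previously able share over 80%, 60% and 40%, and used 80% versus 90% or 65% versus 80% afterwards among the able. The ratio runs from 1.5 to 4.2 with no gains, and from 1.2 to 1.7 with gains of 15% versus 30%.

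**Chance imbalance.** The SD of the difference in prior ability is √[0.6 × 0.4 × (1/84 + 1/122)] = 6.9 points. About 0.85 × 6.9 = 5.9 points carries into the unadjusted difference in Case A, where the true difference is 6 points.

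**Power and type I error.** A second simulation used 95 per condition (effective 190, split equally) and 65% versus 80% among the able.

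| Previously unable | Gains among them | Unadjusted | Adjusted | Restricted |
|---|---|---|---|---|
| 20% | none | 38% | 55% | 55% |
| 40% | none | 24% | 45% | 46% |
| 40% | 15% vs 30% | 55% | 68% | 45% |

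With no treatment effect, every analysis rejected 4.8% to 5.2% of the time.

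**The case against.** Four arguments on the other side deserve weight.

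**The plan already promises adjustment.** The clause covers any confounder found dissimilar between periods, and its list is open. That gives some cover against imbalance. But it sets no threshold, depends on the data, and does not name these variables. It also recovers none of the precision when the periods happen to look alike.

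**The previously unable may respond.** A reader might infer that they form a fixed block of no answers that dilutes the effect. The documents do not say so. It is plausible for long-term non-drivers but weak for walking, which is what the program trains and which may have been lost shortly before admission. Aim 1 also counts improvement beyond the pre-hospital level. For the same reason, the claim that both hypotheses lose most of their information is not supported: that depends on the assumed rates and on no gains.

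**Randomisation protects the test.** This stands. A reader might infer that imbalance in prior drivers would produce a false program effect. Chance imbalance is already in the standard error, and type I error held near 5% in the simulation. With only nine wards, imbalance could be larger than these individual-level figures suggest.

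**An all-patient yes/no comparison is legitimate.** It is, and the fix keeps it. Making the previously able the main analysis set would drop gains that Aim 1 counts and can lose power (Case B). It would also define that set by an item that may be answered after sessions have begun, or skipped, since staff may postpone or omit assessments. That sits badly with the intention-to-treat commitment.

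**Conclusion.** The point holds as a loss of precision in two secondary outcomes, not as a bias. Both documents leave out a baseline value that the trial collects and that Aim 1 refers to. Under the main assumptions, adjustment cuts the variance of the treatment difference about 3-fold with no gains among the previously unable, and about 1.6- to 1.7-fold with gains of 15% versus 30%. Over the wider set of assumed rates, the ratio runs from 1.2 to 4.2. Adjustment gave a smaller variance than the unadjusted comparison in every scenario tried; restriction to the previously able did not always help.

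The figures are for one visit, without clustering or time trends. The stepped-wedge terms would lower the absolute powers quoted. The ability rates are assumptions and should be replaced by the sponsor's own baseline data.

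**What to change.** In Aim 1 of the Protocol's Analytic Approach and of the SAP:

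- **Main analysis.** Pre-specify pre-admission driving as a covariate in the driving model, and pre-admission quarter-mile ability in the walking model. Keep all patients in both.
- **Supporting analyses.** Report keeping or regaining the ability among the previously able, and new gains among the previously unable.
- **Baseline item.** State that the Table 3 question refers to the time before admission, and move it to the day-1 battery so that it is recorded before the first session.

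The multiple imputation already planned for missing predictors can cover missing answers to this item.

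This is a free improvement. It costs a few sentences in each document and moves a one-minute question to an earlier day. For patients already enrolled, use the recorded answers and note when they were taken.
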